### **5. Eligibility Criteria:**

Inclusion criteria - patients must fulfill all of the following to be enrolled on the study:

- Ages 18- 65
- A diagnosis of non-metastatic stage I-III breast cancer of at least 10 mm within the past 90 days, confirmed by a core biopsy
- Patient who is planning to undergo definitive surgery including mastectomy or breast

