## A Pilot “Window of Opportunity” Neoadjuvant Study of Propranolol in Breast Cancer

Principal Investigator: [name]

Co-Principal Investigator: [name], MBA

standard of care on the pre-treatment tissue using an anti-Ki67 antibody (Abcam) based on protocols previously established in the [name] Lab. The post-treatment Ki-67 will be performed in [name] lab. This procedure is a standardized IHC method consistent with those utilized by all in-house TTUHSC pathologists. Ki-67 based proliferative index will be quantified via manual counting by an individual who is blinded to the tumor data on the same specimen and to the corresponding Ki-67 staining in the sample pair. A fixed number of 400 tumor cells in both the initial biopsies and post-treatment surgical samples will be counted from representative areas of the tumor. Comparison of positive and negative controls will be performed for quality assurance. Ki-67 is one of the most robust biomarkers that measures proliferation and according to the International Ki-67 in Breast Cancer Working Group could be important both in standard clinical practice and, particularly, within clinical trials [6]. We recently conducted a study to correlate between Ki-67, Recurrence score (RS) and Recurrence Score –Pathology – Clinical (RSPC) Assessment in Early Stage Breast Cancer and found significant concordance especially among the low and high risk groups [7]. Ki-67 staining shows relatively consistent measurements in specimens across a range of conditions used in routine fixation, tissue processing, and IHC analysis.

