**A Pilot “Window of Opportunity” Neoadjuvant Study of Propranolol in Breast Cancer**  
**Principal Investigator: [name]**  
**Co-Principal Investigator: [name], MBA**

conserving surgery

D) Medically able to abstain from alcohol and all illicit drugs, and limit caffeine intake to less than or equal to 2 cups of coffee per day for at least two weeks before and during the treatment period.

E) Potential subjects systolic blood pressure must be >90 mmHg and/or diastolic > 50 mmHg and no more than 95 mmHg.

F) Able to read, understand and sign a consent form

G) Normal baseline EKG

Exclusion criteria: - patients will be excluded for any of the following criteria:

A) Pregnancy; potential subjects of female bearing age will have to complete a pregnancy test during screening to ensure that they are not pregnant. Potential patients who are post-menopausal must have confirmed one year without menstrual cycle.

B) Free of major medical illnesses including:

- Cardiac diseases (history of cardiac valve disease, coronary artery disease, congestive heart failure, A-V block, peripheral vascular disease, any cardiac arrhythmia/bradycardia) with the exception of the diagnosed cancer.

C) Histories of asthma, bronchospastic disease, or obstructive pulmonary disease

E) Previously diagnosed thyrotoxicosis

F) Severe allergic reactions to medications which are included in the beta blocker family

G) Currently treated with a beta adrenergic receptor antagonist

H) Patients with breast cancer not amenable to surgical resection

I) Patients taking any of the following medications will be excluded:

Input

- Drugs that are categorized as beta-blockers
- Amiodarone
- Sotalol

J) If patient is scheduled to receive surgery in less than 3 weeks of biopsy, then patient will not be eligible.

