### **6. Investigational Plan**

This pilot study is looking to enroll 30 patients total at Texas Tech University Health Sciences Center.

- Once a patient is deemed eligible by the criteria listed above and they sign an informed consent, study treatment will begin. Since we are utilizing the window of opportunity method, it is imperative that we catch patients in the 3 week window from when the patient is diagnosed with breast cancer to when the surgery is scheduled to remove the cancer.
- Participants will remain on 1.5 mg/kg/day of Propranolol, which will be taken twice daily, for 2 weeks and 4 days. The patient will be asked to start a tapering period on day 5 of week 2 and their dose will be lowered by 50%. On day one of week 3, patients will be asked to lower their dose again by 25% of their original dose and they will take the medication at this dose for 4 days. After day 4, the patient will no longer take the medication.[11].
- Patient’s first dose will be in the morning the day after the study medication is distributed to them so that it allows study staff to contact the patient 4-6 hours after they are scheduled to start taking the medication in order to assess toxicities.
- All data points that will be collected will be entered in to the database REDCap.
- All patient visits will be completed at the Garber Breast Care Center at the Texas Tech University Health Sciences Center.

Once a patient signs the appropriate consent and is enrolled in the study, treatment will begin. [name] lab will collect a sample of the biopsied mass and his lab will complete the biomarker assessment on the tissue. Ki-67 assessment is routinely done at the Pathology Department. The baseline study visit will include a physical exam, vitals, electrocardiogram and Eastern Cooperative Oncology Group (ECOG) performance assessment which will be completed by study staff. The subject will be administered the study drug, propranolol. The subject will also receive detailed instructions on how to self-administer the propranolol and be given a medication diary so that they can keep track of when they take the medication. The subject will be provided a blood pressure monitor with a pulse feature included in order to take their blood pressure and pulse twice daily while they are enrolled on the study. When patients are supplied the blood pressure machine

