**A Pilot “Window of Opportunity” Neoadjuvant Study of Propranolol in Breast Cancer**  
**Principal Investigator: [name]**  
**Co-Principal Investigator: [name], MBA**

who will determine any abnormality that would preclude participation. Patients with a normal EKG will be allowed to participate on this trial. After taking the initial dose of propranolol, the study staff will contact the study participant via phone within 4-6 hours in order to follow-up and determine if the patient is having any side effects from the medication. If the patient is found to have side effects, the study staff that conducts the call will immediately notify the PI and/or co-investigators. They will then determine if the study treatment should continue or if the patient should stop treatment. Patients will also be asked to call the study coordinator at any time during the study if they have any further side effects.

In addition to in-clinic assessments, blood pressure and pulse monitoring will be performed and recorded by the participants in-home on a daily basis, twice daily, using supplied monitors to ensure that propranolol is not adversely affecting their blood pressure levels or pulse below established threshold levels. If the blood pressure of any participant drops below 100/60 and/or pulse is <55, propranolol will be stopped and the patient taken off protocol. The event will be counted as an adverse event.

A board certified cardiologist ([name]) who is on active staff at UMC and Texas Tech University Health Sciences Center will review the history and physical exam data, and the EKG to assure that the patient is unlikely to have pre-existing cardiac disease. The cardiologist will also be available throughout the study in order to see patients as needed if the PI and sub-investigators determine it would be beneficial to the patient.

All toxicities will be graded according to CTCAE 4.0. The dose of Propranolol will not be modified. If a patient is found to have an AE grade of 2 or more, treatment will stop and the patient will complete the end of treatment visit.

Study treatment will continue 25 days until there is an unacceptable toxicity, the subject is non-compliant with trial procedures or if the principal investigator and co-investigators feel that it is unsafe for the patient to continue with the treatment.

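### The 90-day diagnosis limit does not fit the 3-week window, and the 3-week surgery rule runs from biopsy rather than first dose, so eligibility does not secure time for the planned course

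*Combined protocol and SAP*

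**What the plan says.** Three statements govern timing.

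- Section 5, second inclusion criterion: "A diagnosis of non-metastatic stage I-III breast cancer of at least 10 mm within the past 90 days, confirmed by a core biopsy".
- Section 5, exclusion J: "If patient is scheduled to receive surgery in less than 3 weeks of biopsy, then patient will not be eligible".
- Section 6, on an interval that ends at the planned operation: "it is imperative that we catch patients in the 3 week window from when the patient is diagnosed with breast cancer".

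The course length is given twice, and the two figures conflict. Section 6 says the drug is taken twice daily, "which will be taken twice daily, for 2 weeks and 4 days", that is 18 days including the taper. Section 8 says "Study treatment will continue 25 days until there is an unacceptable toxicity". Section 6 also sets the start: the patient's "first dose will be in the morning the day after the study medication is distributed to them".

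The primary endpoint (section 9) is the change in proliferative index. Section 4 takes its two measurements from the diagnostic core and the resection: "A fixed number of 400 tumor cells in both the initial biopsies and post-treatment surgical samples will be counted". The documents describe no second biopsy at enrolment, no minimum time from enrolment or first dose to surgery, no minimum exposure for the primary analysis, and no control group.

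**The concern.** The endpoint is meant to capture what a course of roughly three weeks does to Ki-67. That requires a baseline taken close to the start of drug and enough time before surgery to finish the course. Eligibility secures neither. A diagnosis may be 90 days old, more than four times the 3-week window (90/21 = 4.3). Exclusion J protects the biopsy-to-surgery interval, and what the endpoint needs protected is first dose to surgery. The section 6 window also runs from diagnosis, so it does not fill the gap.

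Two things are at stake. Untreated change between core and first dose enters the primary endpoint, and without a control group it cannot be separated from drug effect. If any patient goes to surgery before completing the course, the mean drug effect is diluted.

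**Working it through.** **1. The plan's own power.** Inputs from section 9: mean change 10, SD 15, n = 25, two-sided 5%, paired t-test. Taking 15 as the SD of the paired differences, the noncentrality is (10/15) × √25 = 3.33 with 24 degrees of freedom. Power is 89.2%, which agrees with the stated figure of more than 85%. The sample size is not in dispute here.

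**2. Does J leave room for the course?** Set biopsy at day 0, dispensing on enrolment day e, first dose on day e + 1, and surgery on day S. I assume the diagnosis date is the biopsy date and that dispensing happens on the enrolment day. Dosing days available before surgery are S − e − 1. J requires S ≥ 21. At S = 21:

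| Enrolment day e | Dosing days, 21 − e − 1 |
|---|---|
| 2 | 18 |
| 10 | 10 |
| 14 | 6 |
| 18 | 2 |

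An 18-day course needs e ≤ 20 − 18 = 2. A 25-day course does not fit at all, since 25 exceeds 21. For e ≥ 21, J is satisfied by elapsed time whatever the surgery date. For example, enrolment on day 90 with surgery on day 95 passes both criteria with 95 − 90 − 1 = 4 dosing days.

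**3. Untreated share when the full course is taken.** With first dose c days after biopsy and a course of L days, the share is c/(c + L). At c = 90:

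- L = 18: 90/108 = 83%.
- L = 25: 90/115 = 78%.

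The share is below one half only when c < L. These are fractions of calendar time at the limit of the criterion.

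**4. Illustration: dilution.** Suppose a fraction f of patients has no response and the rest respond by 10. The mean is 10(1 − f) and the SD is √(225 + 100f(1 − f)), which includes the variance from mixing the two groups. At n = 25:

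| f | Mean | SD | Power |
|---|---|---|---|
| 0 | 10 | 15.0 | 89% |
| 10% | 9 | 15.3 | 81% |
| 20% | 8 | 15.5 | 70% |
| 40% | 6 | 15.8 | 45% |

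**5. Illustration: drift.** Suppose the drug has no effect, but the index moves by 2, 3 or 5 points on average between core and resection. With SD 15 and n = 25, the planned test rejects 10%, 16% or 36% of the time instead of 5%.

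The fractions in step 4 and the drifts in step 5 are assumptions. The documents give neither.

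**The case against.** The best reply is that sections 6 and 8 each prescribe a fixed course, so a patient whose surgery falls a few days after dispensing could not follow the treatment plan and staff would probably not start her. This stands. A reader might infer from the criteria that the trial will enrol patients with only days on drug. The documents do not support that: such a patient passes eligibility but departs from the planned course under either stated length. What remains is that no eligibility criterion turns her away and no analysis rule says how to handle her.

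A reader might also take 83% or 78% as the size of a bias. They are not. They are worst-case shares of elapsed time, and nothing in the documents says how far Ki-67 moves without treatment.

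Nor do the documents show that power is lost. The fractions in step 4 are assumed, and zero response is the harsh end. If under-exposed patients kept half the effect, 10% or 20% of them would leave a mean of 9.5 or 9.0, and power of about 86% or 81% with mixing variance included.

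Finally, a before-and-after comparison without controls cannot separate drift from drug effect at any interval. That is correct. A shorter interval reduces the exposure to drift but does not remove it. The objection does not touch the inconsistency between the 90-day limit and the 3-week window, or the fact that J is counted from the wrong date for protecting treatment time.

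**Conclusion.** The point holds as a gap in the eligibility rules. The 90-day limit and the 3-week window cannot both describe the intended population, and J does not secure time for the planned course. At its minimum interval, an 18-day course fits only with enrolment by about day 2, and J has no force for anyone enrolled 3 or more weeks after biopsy. Choosing between 18 and 25 days would not close the gap.

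The firmer consequence is the old baseline, because it arises even when every patient completes the course: up to 83% or 78% untreated time at the limit. Short exposure is the weaker one. The effect on the trial's result cannot be sized from the documents, because the number of late enrolees and the untreated Ki-67 drift are unknown. The power and false-positive figures show sensitivity under stated assumptions and are not forecasts. It would be too much to say that the trial cannot answer Aim 1; the problem affects the patients enrolled late or with early surgery, however many they are. The change is cheap and should be made.

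**What to change.** - **Exclusion J.** Count it from the planned first dose, so that a patient is ineligible if surgery is already planned before the end of the planned course. Use the course length the sponsor settles on after reconciling sections 6 and 8. The rule screens patients; it should not be read as a reason to move a surgery date.
- **Second inclusion criterion.** Reconcile the 90-day limit with the section 6 window. The sponsor should set the value and state whether it runs to enrolment or to first dose.
- **Data.** Record days from biopsy to first dose and days on drug for every patient.
- **Analysis.** Add sensitivity analyses of the primary endpoint by these two intervals, including one restricted to patients who completed the planned course. That restricted analysis is supportive only, because section 8 stops treatment for toxicity and completers are therefore a selected group.

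The cost is an amendment to two eligibility lines, a short addition to section 9, and two derived variables. The biopsy and first-dose dates should be available from routine records; days on drug must come from the medication diary. The real downside is a somewhat smaller eligible pool at a single centre seeking 30 patients. The documents do not allow that loss to be estimated.

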**A Pilot “Window of Opportunity” Neoadjuvant Study of Propranolol in Breast Cancer**  
**Principal Investigator: [name]**  
**Co-Principal Investigator: [name], MBA**

conserving surgery

D) Medically able to abstain from alcohol and all illicit drugs, and limit caffeine intake to less than or equal to 2 cups of coffee per day for at least two weeks before and during the treatment period.

E) Potential subjects systolic blood pressure must be >90 mmHg and/or diastolic > 50 mmHg and no more than 95 mmHg.

F) Able to read, understand and sign a consent form

G) Normal baseline EKG

Exclusion criteria: - patients will be excluded for any of the following criteria:

A) Pregnancy; potential subjects of female bearing age will have to complete a pregnancy test during screening to ensure that they are not pregnant. Potential patients who are post-menopausal must have confirmed one year without menstrual cycle.

B) Free of major medical illnesses including:

- Cardiac diseases (history of cardiac valve disease, coronary artery disease, congestive heart failure, A-V block, peripheral vascular disease, any cardiac arrhythmia/bradycardia) with the exception of the diagnosed cancer.

C) Histories of asthma, bronchospastic disease, or obstructive pulmonary disease

E) Previously diagnosed thyrotoxicosis

F) Severe allergic reactions to medications which are included in the beta blocker family

G) Currently treated with a beta adrenergic receptor antagonist

H) Patients with breast cancer not amenable to surgical resection

I) Patients taking any of the following medications will be excluded:

Input

- Drugs that are categorized as beta-blockers
- Amiodarone
- Sotalol

J) If patient is scheduled to receive surgery in less than 3 weeks of biopsy, then patient will not be eligible.

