**Toxicity and Adverse Events**

Known side effects of propranolol include hypoglycemia, hypotension, bradycardia, and bronchospasm. It was recently reported in a study of over 460 patients with infantile hemangioma that a dose of propranolol up to 3 mg/kg/day for up to 6 months resulted in no significant difference in adverse events between the placebo and treatment group [9]. Safety assessments will be performed at in-clinic visits by analysis of adverse events (i.e. any change in condition between the time of informed consent and the end of the trial); laboratory investigations (including measurement of glucose levels from finger-prick blood samples), physical examination (including pulmonary auscultation, liver palpation, assessment of vital signs, and assessment of cognitive function), and electrocardiography.

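### The blood-pressure entry floor (90/50) lies 10 mmHg below the off-protocol limit (100/60) on each component, so a patient at 95/55 can be enrolled and dosed while already under the stop limit

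*Combined protocol and SAP*

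**What the plan says.** Section 5, inclusion E, sets the entry range: "Potential subjects systolic blood pressure must be >90 mmHg and/or diastolic > 50 mmHg and no more than 95 mmHg".

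Section 8 (Toxicity Monitoring and Dose Modification) sets the on-study limit: "If the blood pressure of any participant drops below 100/60 and/or pulse is <55, propranolol will be stopped and the patient taken off protocol". It adds: "The event will be counted as an adverse event". Pressure and pulse are measured at home twice a day.

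Dosing is the same for everyone. Section 6 states: "Participants will remain on 1.5 mg/kg/day of Propranolol, which will be taken twice daily, for 2 weeks and 4 days", with a step-down that begins on day 5 of week 2. Section 8 rules out adjustment: "The dose of Propranolol will not be modified". Treatment starts once the patient is eligible and has consented, with the first dose on the morning after the drug is handed out.

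Section 7 (Toxicity and Adverse Events) lists the relevant risk: "Known side effects of propranolol include hypoglycemia, hypotension, bradycardia, and bronchospasm". It describes an adverse event as "any change in condition between the time of informed consent and the end of the trial".

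**The concern.** Propranolol can lower blood pressure, so the entry floor should be at or above the level at which the drug is withdrawn. Here the order is reversed, and nothing in the protocol reconciles the two limits.

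The first issue is safety. A patient with low pressure receives the same weight-based dose as everyone else, with no lower starting dose and no option to reduce it. The second is data quality. Aim 3 is safety, toxicity and adherence, and a pressure that was low before the first dose could be recorded as an event on propranolol. The patient also takes one of 30 places and then leaves the protocol under a rule that could have been applied at screening.

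**Working it through.** The plan gives no figure to reproduce. The check compares the two rules directly.

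**Inputs**
- Entry (Section 5, inclusion E): systolic S > 90 and/or diastolic D > 50, with an upper limit of 95, taken here as diastolic. The reading 95/55 satisfies that upper limit whichever component it applies to.
- Stop (Section 8): below 100/60.
- Dose (Section 6): 1.5 mg/kg/day. Planned enrolment: 30.

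**Gap.** Systolic 100 − 90 = 10 mmHg. Diastolic 60 − 50 = 10 mmHg.

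**Example pressures under each reading**

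| Pressure | Eligible, *and* | Eligible, *or* | Under limit, both components | Under limit, either component |
|---|---|---|---|---|
| 95/55 | yes | yes | yes | yes |
| 91/51 | yes | yes | yes | yes |
| 99/59 | yes | yes | yes | yes |
| 110/55 | yes | yes | no | yes |
| 95/70 | yes | yes | no | yes |
| 85/55 | no | yes | yes | yes |
| 95/45 | no | yes | yes | yes |
| 100/60 | yes | yes | no | no |

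On the reading least favourable to the concern (*and* at entry, both components at stop), the overlap is S from 91 to 99 with D from 51 to 59: 9 × 9 = 81 whole-number pairs. If entry required S ≥ 100 and 60 ≤ D ≤ 95, the overlap would be 0 pairs on either reading of the stop rule.

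**What follows for a patient at 95/55.** There are two alternatives.
1. *100/60 is an absolute level.* The patient must be stopped at the first home reading unless pressure has risen. Exposure is short. A home reading before the first dose is possible but not required.
2. *The rule means a fall from above 100/60.* The blood-pressure limit never applies to this patient. What remains is the pulse limit (below 55), the stop for any adverse event of grade 2 or more, and the stop when the investigators "feel that it is unsafe for the patient to continue with the treatment".

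**Other safeguards.** Baseline vital signs carry no limit beyond inclusion E. The cardiologist looks for pre-existing cardiac disease. The 4-6 hour call comes after the first dose. The safety board is given no pressure threshold. None of these sets a numeric blood-pressure floor.

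**Dose, before tablet rounding.** At assumed weights of 50, 70 and 90 kg, 1.5 mg/kg/day gives 75, 105 and 135 mg/day. Section 7 gives the usual initial dose for hypertension as 2 × 40 = 80 mg/day, which the trial dose exceeds above 80 / 1.5 = 53.3 kg.

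**Number affected.** No baseline pressure distribution is given. With an assumed share p of eligible patients under the limit, the expected number is 30p and the chance of at least one is 1 − (1 − p)^30:

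| p (assumed) | Expected of 30 | Chance of at least one |
|---|---|---|
| 1% | 0.3 | 26% |
| 5% | 1.5 | 79% |
| 10% | 3.0 | 96% |

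**The case against.** The strongest reply accepts the mismatch and disputes how much it matters.

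- **An absolute limit is the natural reading.** Just before the stop rule, Section 8 says home monitoring is there to keep pressure and pulse from going under set limits. This makes reading 1 likelier, and the absence of any numeric pressure stop (reading 2) should not carry equal weight. The point stands, but the wording of the rule still carries a sense of change, so the question is not settled.
- **Under that reading the harm is small.** Twice-daily readings should remove the patient within about a day, and staff call after the first dose. This also stands. What remains is a brief avoidable exposure, a wasted place and an adverse event of doubtful attribution. That attribution is itself arguable, because Section 7 defines an adverse event as a change after consent.
- **The dose comparison is selective.** Section 7 also gives 120 to 240 mg/day as usual maintenance for hypertension and 40 mg three times daily (120 mg/day) as the initial dose after myocardial infarction. At 70 kg the trial dose of 105 mg/day is below both. The taper also covers 7 of the 18 days described in Section 6. This is fair: the dose is not unusual. It shows only that the protocol has no lower dose for a low-pressure patient.
- **The counts do not measure frequency.** The 81 pairs describe the overlap between the rules, and the shares are assumptions with no anchor in the documents. This stands, and the conclusion does not rest on them.
- **A floor of exactly 100/60 leaves no headroom.** A patient entering at 100/60 leaves the protocol after a 1 mmHg fall. This is true, and is a reason to say *at least* 100/60. It does not defend the present floor.

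None of this removes the contradiction at 95/55.

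**Conclusion.** The concern holds, and the rule is wrong as written. The entry floor is 10 mmHg below the stop limit on each component, and 95/55 falls in the gap on every reading of both rules. On the likelier reading the protocol enrols and may dose a patient whom its own rule then removes. On the less likely one it leaves that patient without a numeric blood-pressure limit.

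The size of the gap is exact. The number of patients affected is unknown, and the 0.3 to 3 of 30 rests wholly on assumed shares of 1% to 10%. The stated power is not in dispute. This should be fixed: the likely exposure is short, but the conflict is avoidable and the correction is simple.

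**What to change.** 1. In inclusion E, replace *and/or* with *and*, and require systolic pressure of at least 100 mmHg together with diastolic pressure of at least 60 and at most 95 mmHg. A higher floor would give headroom, if the sponsor wants it.
2. In Section 8, state whether 100/60 refers to either component or both, and that it is an absolute level if that is what is meant.
3. Do not close the gap by lowering the stop limit to 90/50, which would weaken protection.

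The cost is protocol wording, with no new visit, test or tissue. Some low-pressure patients who are now eligible would be excluded, including those such as 110/55 who are low on one component only. Their number cannot be derived from the documents. At the assumed 1% to 10% it is 0.3 to 3 per 30 otherwise eligible patients, who would have to be replaced to reach 30.

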**Contradictions**

## A Pilot “Window of Opportunity” Neoadjuvant Study of Propranolol in Breast Cancer

Principal Investigator: [name]

Co-Principal Investigator: [name], MBA

Propranolol is contraindicated in 1) cardiogenic shock; 2) sinus bradycardia and greater than first degree block; 3) bronchial asthma; and 4) in patients with known hypersensitivity to propranolol hydrochloride.

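### Exclusion criterion B has reversed polarity: as written, it excludes patients who are free of cardiac disease

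*Combined protocol and SAP*

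**What the plan says.** In Section 5 (Eligibility Criteria), the lead-in to the exclusion list is "Exclusion criteria: - patients will be excluded for any of the following criteria". Item B under it reads "B) Free of major medical illnesses including", followed by a bullet that starts "Cardiac diseases (history of cardiac valve disease, coronary artery disease, congestive heart failure, A-V block, peripheral vascular disease, any cardiac arrhythmia/bradycardia" and closes with "with the exception of the diagnosed cancer".

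Three other places bear on the same patients:

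- Section 5, inclusion criterion G, requires a normal baseline EKG. Section 8 repeats that a normal EKG allows participation.
- Section 8 (Toxicity Monitoring and Dose Modification) has a board-certified cardiologist look at the history, the examination findings and the EKG "to assure that the patient is unlikely to have pre-existing cardiac disease".
- Section 7 (Drug Information) states: "Propranolol is contraindicated in 1) cardiogenic shock; 2) sinus bradycardia and greater than first degree block; 3) bronchial asthma". It adds known hypersensitivity as a fourth item.

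Section 6 (Investigational Plan) starts study treatment once a patient has been found eligible on the Section 5 criteria and has consented.

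**The concern.** In an exclusion list, meeting an item keeps the patient out. Item B makes freedom from cardiac disease the thing to be met. A patient with no cardiac history therefore meets an exclusion, and a patient with heart failure or A-V block does not meet it.

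This matters because the wording is operative. Section 6 makes the Section 5 criteria the route to propranolol, and B is the only exclusion that names cardiac disease in a trial giving a beta-blocker to breast cancer patients. Section 10 also has the study team audit its own conduct against the approved protocol, so the written criterion is the standard that conduct is compared with. A rule that has to be read against its own words is a poor standard for either purpose.

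**Working it through.** No arithmetic applies, and the plan gives no figure to reproduce. The check sets the texts side by side.

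**Step 1: the literal logic of B.** Lead-in: excluded if any item is met. Item B: free of the listed diseases. Combined: excluded if free of the listed diseases.

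**Step 2: B against the other exclusions.** The lettered exclusions are A, B, C, E, F, G, H, I and J, nine in all (the list has no D). Items C and E to J each name the disqualifying condition directly. Item A does so too (pregnancy), although it carries a supporting requirement about menopausal status phrased as something the patient must satisfy. B is the only one of the nine whose main condition is the desired state.

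**Step 3: what the wording suggests was meant.** The closing words "with the exception of the diagnosed cancer" make sense after a requirement to be free of illness: the patient must be free of major illness, other than the cancer. They make no sense after a condition that excludes. B looks like inclusion wording placed in the exclusion list.

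**Step 4: what happens to each kind of patient.**

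| Patient | Exclusion B as written | Inclusion G (normal EKG) | Section 8 cardiologist review |
|---|---|---|---|
| No listed cardiac disease, normal EKG | Excluded | Passes | Passes |
| History of a listed condition, normal EKG | Not excluded | Passes | Should be stopped |
| Listed condition, abnormal EKG | Not excluded | Fails | Should be stopped |

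The first row is the intended population, and B removes it. In the second row, the Section 8 review is the only remaining barrier directed at the cardiac history. The exclusions for beta-blockers, amiodarone and sotalol would catch some treated cardiac patients, but because of the drug and not the history.

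**Step 5: overlap with the Section 7 contraindications.** Section 7 lists four items.

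- Cardiogenic shock: not named in B.
- "sinus bradycardia and greater than first degree block": overlaps with A-V block and bradycardia in B.
- Bronchial asthma: covered by exclusion C, which is correctly worded.
- Hypersensitivity to propranolol: severe reactions to beta-blockers are covered by exclusion F, also correctly worded.

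So one of the four items conflicts with B as written.

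**The case against.** The strongest reply is that nobody could run the trial on the literal reading. Patients without cardiac disease would meet B, those with it should fail the Section 8 review, and almost no one would be left. The closing words of B show what was meant. The trial runs at one institution, with all visits at one clinic and the reviewing cardiologist on the institution's staff, so divergent readings across sites are not at issue. This stands as an argument about severity, but it does not make the criterion correct as written.

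A reader might go further than the documents allow in four ways.

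- *That the protocol admits cardiac patients.* Not meeting an exclusion does not admit anyone. Inclusion G and the Section 8 review still stand, and the review covers history and examination as well as the EKG. These safeguards are partial: the review sits outside Section 5, aims to make cardiac disease unlikely, and states no rule that a listed history excludes.
- *That all 30 planned patients would be wrongly excluded or logged as deviations.* That follows only if staff apply B literally, and nothing in the documents suggests that they would.
- *That the REDCap form carries the reversed logic.* No eligibility form or checklist appears in the documents. REDCap is described only as the system for collected data.
- *That B contradicts the Section 7 contraindications generally.* Only sinus bradycardia and greater than first-degree block overlap. Section 7 also lists angina, atrial fibrillation and post-infarction use among the drug's indications, so it does not support keeping out every condition that B names. For the rest of the list, the conflict is with Section 8.

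**Conclusion.** The polarity error is real and is in the current text. As written, B excludes the intended patients, and no Section 5 exclusion removes patients for a history of the listed cardiac conditions. It conflicts with the purpose of the Section 8 review and with one of the four Section 7 contraindication items.

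The size is limited. One criterion is affected, its intent is recoverable, two partial safeguards remain, and sample size, power, significance level and intended population are untouched. This is a drafting error in an operative safety criterion. It is not a design flaw, and it is no evidence that any patient was or would be wrongly enrolled. It should still be corrected, because Section 5 decides who starts treatment.

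The conclusion assumes that B was meant as a requirement to be free of the listed diseases, which its closing words and Section 8 both indicate. The investigator should confirm this.

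**What to change.** Reconcile B with its lead-in and with Section 8 in one of two ways:

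- restate B as a condition that excludes, naming the presence or history of the same listed diseases; or
- move B unchanged to the inclusion list, whose lead-in requires every item to be met, so that the present wording takes its evident meaning.

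The disease list need not change under either option. If the first is chosen, the closing words about the diagnosed cancer should be checked, since they were written for the opposite polarity. Any eligibility checklist or data-entry form derived from Section 5 should use the same polarity as the amended text.

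The cost is one amended line and a check of any derived form. Visits, sample size, analysis and the population the trial intends to enrol all stay as they are.
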